9.5.4 Study drug supply

The sponsor will arrange delivery of ixazomib citrate to trial sites. No investigational medicinal product will be shipped until the sponsor has verified that all regulatory required documents and approvals for the site are available.

Ixazomib citrate will be provided as unlabeled bulk drug by Millennium The Takeda Oncology Company to the central pharmacy in the VU University Medical Center Amsterdam, where the drug

will be labeled. From the central pharmacy in the VU University Medical Center Amsterdam the drug will be shipped refrigerated to the pharmacy at the study sites.

9.5.5 Drug accountability

When ixazomib citrate capsules are dispensed to the patient for take-home dosing, patients should be instructed to return their empty blister packs to the trial site, rather than discarding them.

Reconciliation will occur accordingly when the patient returns for their next cycle of take-home medication.

The investigator, or a pharmacist or other appropriate individual who is designated by the investigator, should maintain records of the product's delivery to the trial site, the inventory at the site, the use by each patient, and the return to the sponsor or alternative disposition of unused product(s). These records should include dates, quantities, batch/serial numbers, expiration dates (if applicable), and the unique code numbers assigned to the investigational product(s) and trial patients (if applicable). Study drug will be administered or dispensed only to eligible patients under the supervision of the investigator or identified sub-investigator(s). Investigators should maintain records that document adequately that the patients were provided the doses specified by the protocol and reconcile all investigational product(s) received from the sponsor.

9.5.6 Study drug return and destruction

Partially used investigational medicinal product should not be redispensed to either the same or another patient after it has been returned.

The trial site should destroy used or partially used study drug containers after drug accountability records have been completed. Destruction should be documented.

At the end of the trial or after expiry of the product unused investigational medicinal product should be destroyed by the trial site according to site's standard procedures. Destruction should be documented.

9.6 Investigational Medicinal Product: Placebo

9.6.1 Summary of known and potential risks

The emerging safety profile indicates that the placebo capsules consisting of microcrystalline cellulose, talc, and magnesium stearate is generably well tolerated with manageable and reversible AEs.

9.6.2 Preparation and labeling

Placebo will be labeled as an Investigational Medicinal Product.

The placebo capsules will be provided by Millennium. The placebo will be labeled. Packaging labels will fulfill all requirements specified by governing regulations. The placebo capsules consists of microcrystalline cellulose, talc, and magnesium stearate.

Capsules should be stored unopened at 2-8°C (36-46°F) and must be administered as intact capsules and are not intended to be opened or manipulated in any way.

9.6.3 Storage and handling

Similar to section 9.5.3

9.6.4 Study drug supply

The sponsor will arrange delivery of placebo to trial sites. No investigational medicinal product will be shipped until the sponsor has verified that all regulatory required documents and approvals for the site are available.

Placebo will be provided by Millennium The Takeda Oncology Company as described for ixazomib citrate in section 9.5.4.

9.6.5 Drug accountability

Similar to section 9.5.5.

9.6.6 Study drug return and destruction

Similar to section 9.5.6.

10 Study procedures

10.1 Time of clinical evaluations

- At entry: before start of treatment (periperheral blood and urine lab values within 6 weeks prior to start, bone marrow and skeletal survey within 8 weeks).
- During induction therapy after 1, 3, 5, 7 and 9 cycles (just before start of the next cycle).
- Before start of maintenance treatment (periperheral blood and urine lab values within 4 weeks prior to start),

- During maintenance therapy after every maintenance cycle during the first year, thereafter every 8 weeks.
- When patient is taken off protocol treatment.
- During follow up every 8 weeks untill second progression and every 6 months thereafter.

All patients will be followed until 8 years after registration.

10.2 Required investigations

Required investigations at entry, during treatment and during follow up

	At entry	After cycles 1,3,5,7,9 (just before start next cycle)	During maintenance after every cycle during the first 12 months, thereafter and during follow up every 8 weeks ²⁾	When going off protocol treatment
Medical history	х	Х	Х	х
Physical examination	Х	х	х	х
Hematology	х	x ¹⁾	Х	х
Blood chemistry	х	Х	Х	х
Immunochemistry	Х	х	х	х
Bone marrow				
Bone marrow aspirate	х	x ³⁾	x ³⁾	х
Bone marrow biopsy	x ⁴⁾	x ⁴⁾	x ⁴⁾	х
Cytogenetic analysis ⁵⁾	х			х
BM cryopreservation	x ⁶⁾	x ⁶⁾	x ⁶⁾	х
Specific investigations				
ISS β ₂ -microglobulin and albumin	х			
Creatinine clearance	х	o.i	o.i	
Skeletal survey or CT	X ⁷⁾	X ^{8,9)}	X ^{8,9)}	
MRI ⁹⁾	o.i.	o.i.	o.i.	
X-thorax	х			
ECG	х			
Additional investigations	o.i.	o.i.	o.i.	
PB cryopreservation	X ¹⁰⁾	X ¹⁰⁾	X ¹⁰⁾	
Quality of Life	х	X ¹¹⁾	X ¹¹⁾	
FDG-PET ¹²	х	X ¹²		

- o.i. on indication
- 1) Hematology every 2 weeks. In case no hematological toxicity occurs in the cycles 1, 2 and 3 every 4 weeks is allowed. As soon as in the following cycles hematological toxicity occurs, the interval will be shortened to 2 weeks.
- 2) During maintenance therapy out clinic visits, hematology, blood chemistry and immunochemistry will be performed every cycle during the first 12 months, thereafter every 8 weeks. After discontinuation of maintenance therapy during follow up visits hematology, blood chemistry and immunochemistry will be performed every eight weeks or at shorter intervals at the discretion of the treating physician until second progression and every 6 months thereafter. During maintenance therapy physical examination will done every 2 cycles.

- 3) In case of confirming CR, at the moment of complete disappearance of serum/urine M-component by immunofixation, or at progression, a bone marrow aspirate and/or bone marrow biopsy is indicated. To confirm stringent CR, either kappa/lambda labeling of a bone marrow biopsy or immunophenotyping of the BM aspirate has to be performed.
 Moreover, the first time of confirming CR, bone marrow has to be send to the central laboratory to determine the MRD status by use of flow cytometry. Please also send material for biological studies to the central laboratory at the time of progression. See appendix I for procedures for collecting and handling of the samples. After a confirmed CR repeated sampling of bone marrow aspirate is no longer necessary. In case the hematologist decides to send a second sample to the central laboratory for MRD analysis and the patient is participating in the PET-CT study, with a positive PET at the first MRD analysis, a PET-CT scan will be repeated at the second MRD analysis. See 12).
- 4) A bone marrow biopsy is optional. In case of first diagnosis or confirming stringent CR at the moment of complete disappearance of serum/urine M-component by immunofixation, either a kappa/lambda labeling of a bone marrow biopsy or immunophenotyping of a BM aspirate has to be performed.
- 5) Cytogenetic analysis will be performed in the cytogenetic reference labs for each local site
- 6) Will be performed at entry, at confirmation of a (s)CR and at progressive disease. See appendix I for procedures for collecting and handling of the samples. The samples have to be sent to the central lab of Erasmus MC.
- 7) Osteolytic lesions observed at total body X-ray or CT (≥1 osteolytic lesion and focal lesions at MRI (at least 2 focal lesions must be 5 mm or more in size) will be criteria for symptomatic MM (see appendix A).
- 8) After completion of induction therapy, in case of confirming (s)CR and when clinically indicated
- 9) In case of (extramedullary) plasmacytoma on MRI or CT, this examination should be repeated at least after cycle 9 of induction treatment and yearly thereafter or in case (s)CR is suggested
- 10) Will be performed at entry and at progressive disease in every patient for future biological studies (during follow up). See appendix I for procedures for collecting and handling of the samples.
- 11) Quality of life at entry, after cycle 3, 6 and 9 (or earlier in case of prematurely discontinuation of induction treatment), after 6 and 12 months of maintenance and at discontinuation of maintenance therapy.
- 12) In patients who gave permission to participate in the FDG-PET study a FDG-PET CT scan will be performed at the following study time points:
- A) At entry and before randomization of maintenance therapy after completion of 9 cycles of induction treatment or after a minimum of 6 cycles in case there is non-hematological toxicity not related to ixazomib citrate, requiring discontinuation of induction therapy;
- B) At the time CR* is reached and MRD assessment in bone marrow by MFC is performed;
- C) in case a second MRD assessment will be performed and FDG-PET negativity (PET-CR or complete metabolic response (CMR)) has not been reached yet, an additional FDG-PET-CT will be performed.
 - * In case CR/sCR are reached before the end of induction therapy and FDG-PET negativity (CMR) has been reached already, no FDG-PET-CT will be performed before randomization of maintenance therapy in case there is no loss of CR/sCR

Medical history

Standard medical history, with special attention for:

- Adverse Events
- WHO performance status
- Bone pain

- Infections
- Bleeding tendency
- Constipation
- Polyneuropathy

Only at entry:

- Occupational history
- Prior and present other diseases
- Antecedent hematological or oncological diseases
- Previous chemotherapy or radiotherapy

Physical examination

Standard physical examination including body weight and height, with special attention for:

- Macroglossia
- Kyphoscoliosis
- Orthostatic hypotension
- Carpal tunnel syndrome
- Polyneuropathy or other neurological symptoms
- Edema
- Infections
- Bleeding tendency

Hematology

Hemoglobin, Leukocyte count, Neutrophil count, Platelets

Blood chemistry

Creatinine, ASAT, ALAT, Total bilirubin, Total proteins, Albumin, LDH, Calcium

Immunochemistry

- At entry: Qualitative and Quantitative serum and urine (24 hrs urine) M-protein, including immunofixation and FLC ratio.
- Evaluation: Qualitative and Quantitative serum and urine (24 hrs urine) M-protein, including immunofixation to confirm CR. FLC ratio only to confirm (s)CR.

Quantitative M-protein in serum and urine by gel electrophoresis preferably. Nephelometry or turbidometry are allowed, see appendix C for instructions.

Qualitative M-protein in serum and urine by immunofixation

Immunofixation and Free Light Chain ratio to determine the achievement of CR and sCR respectively

Bone marrow

Bone marrow aspiration (obligatory) and biopsy (optional) at entry, including (molecular) cytogenetic evaluation.

Repeated bone marrow aspiration (biopsy is optional) in case the decline in M-protein suggest achievement of CR or sCR (see appendix C for response ciriteria) or at progressive disease/relapse.

- Bone marrow aspirate at entry for:
- Morphology
- FISH analysis: see section 10.5
- Immunophenotyping has to be performed at entry in case no BM biopsy is performed in order to determine the presence of monoclonal plasmacells.
- Bone marrow aspirate at response evaluation for confirmation of CR, flowcytometry analysis to determine MRD and molecular studies.
- Bone marrow aspirate at progressive disease for confirmation of progression and molecular studies.
- Bone marrow biopsy at entry and to confirm (stringent) complete response, including kappa lambda labeling. In case no BM biopsy is performed the presence of monoclonal plasmacells at entry or a stringent CR has to be confirmed by kappa/lambda labeling using immunophenotyping of the BM aspirate. After a confirmed CR repeated sampling of bone marrow aspirate is no longer necessary.

Radiographic assessment of lytic bone lesions (either X-ray or whole body CT) at entry, after completion of induction therapy and in case of confirming (s)CR

If an MRI is performed at entry and found positive it should be repeated after induction chemotherapy and in case CR is suggested

Additional investigations

Only on clinical indication:

- Survey for exclusion of AL amyloidosis
- aPTT, PT(INR).
- In case of prolonged aPTT and/or PT(INR) a factor X activity has to be determined
- Cryoglobulins, cold agglutinins
- Fundoscopy
- Spirometry

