8.1.1 Inclusion criteria

- Previously untreated patients with a confirmed diagnosis of symptomatic multiple myeloma according to IMWG criteria (see appendix A)
- Measurable disease according to the IMWG criteria (see appendix A)
 (If plasmacytoma is the only measurable parameter, the patient is not allowed to be included in the study, because of difficult response evaluation)
- Age ≥ 66 years or patients ≤ 65 years not eligible for ASCT
- WHO performance status 0-3 for patients <75 years and WHO performance status 0-2 for patients ≥ 75 years (see appendix D)
- Absolute neutrophil count (ANC) ≥ 1.0 x10⁹/l and platelet count ≥ 75x10⁹/l, unless related to bone marrow infiltration by malignant plasmacells
 Platelet transfusions to help patients meet eligibility criteria are not allowed within 3 days before study enrollment
- Written informed consent
- Patient gives consent for extra bone marrow and blood sampling
- Negative pregnancy test at study entry or at least 1 year post-menopausal or surgically sterile before study entry
- ◆ A female patient of childbearing potential, agrees to practice 2 effective methods of contraception, at the same time, from the time of signing the informed consent through 90 days after the last dose of study drug, AND must also adhere to the guidelines of any treatment-specific pregnancy prevention program (for thalidomide) OR agrees to completely abstain from heterosexual intercourse. (Periodic abstinence (eg, calendar, ovulation, symptothermal, post-ovulation methods) and withdrawal are not acceptable methods of contraception)

♦ Male patients, even if surgically sterilized, (i.e., status post vasectomy) must agree to practice effective barrier contraception during the entire study period and through 90 days after the last dose of study drug, AND must also adhere to the guidelines of any treatment-specific pregnancy prevention program (for thalidomide), OR agrees to completely abstain from heterosexual intercourse (Periodic abstinence (eg, calendar, ovulation, symptothermal, post-ovulation methods] and withdrawal are not acceptable methods of contraception).

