
A. Criteria for symptomatic MM and measurable disease

S.V. Rajkumar et al. (The Lancet Oncology, 2014: 15; e538-e548)

Criteria for symptomatic MM

Clonal bone marrow plasma cells ≥10% or biopsy-proven bony or extramedullary plasmacytoma¹

AND any one or more of the following myeloma defining events or biomarkers of malignancy, specifically:

Myeloma defining events

Evidence of end organ damage that can be attributed to the underlying plasma cell proliferative disorder:

- Hypercalcemia: serum calcium >0.25 mmol/l (>1 mg/dl) higher than ULN or >2.75 mmol/l (>11 mg/dl)
- Renal insufficiency: creatinine clearance² <40ml/min or serum creatinine >177 μmol/l (>2 mg/dl)
- Anemia: (hemoglobin >2 g/dl below normal limit of or hemoglobin <10 g/dl)
 (hemoglobin >1.24 mmol/l below normal limit of or hemoglobin <6.21 mmol/l)
- Bone lesions: one or more osteolytic lesions on skeletal radiography, CT, or PET-CT³

Biomarkers of malignancy:

- Clonal bone marrow plasma cell percentage¹ ≥60%
- Involved: uninvolved serum free light chain ratio⁴ ≥100
- >1 focal lesion⁵ on MRI studies

Footnotes:

- 1. Clonality should be established by showing κ/λ light-chain restriction on flow cytometry, immunohistochemistry, or immunofluorescence. Bone marrow plasma cell percentage should preferably be estimated from a core biopsy specimen; in case of a disparity between the aspirate and the core biopsy, the highest value should be used.
- 2. Measured or estimated by validated equations.
- 3. If bone marrow has less than 10% clonal plasma cells, more than one bone lesion is required to distinguish from solitary plasmacytoma with minimal marrow involvement.
- 4. These values are based on the serum Freelite assay (The Binding Site Group, Birmingham UK). The involved free light chain must be ≥100 mg/L.
- 5. At least 2 focal lesions must be 5 mm or more in size.

Criteria for measurable disease

Serum M-protein ≥ 10 g/L or

Urine M-protein \geq 200 mg/24 hours **or**

Abnormal FLC ratio with involved free light chain (FLC) > 100 mg/L or

Proven plasmacytoma by biopsy *

^{*} If plasmacytoma is the only measurable parameter, the patient is not allowed to be included in the study, because of difficult response evaluation.

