B. International Staging System for Multiple Myeloma (ISS stage)

International Staging System for Multiple Myeloma of the International Myeloma Working Group (J Clin Oncol 2005: 23; 3412-3420).

Stage Criteria

I Serum β_2 -microglobulin < 3.5 mg/L **and**Serum albumin \geq 3.5 g/dL

II Neither stage I nor stage III*

III Serum β_2 -microglobulin \geq 5.5 mg/L

^{*} There are two categories for stage II: serum β_2 -microglobulin < 3.5 mg/L but serum albumin < 3.5 g/dL; or serum β_2 -microglobulin 3.5 to < 5.5 mg/L irrespective of the serum albumin level.

C. Response criteria for Multiple Myeloma

Based on Consensus recommendations for the uniform reporting of clinical trials: report of the International Myeloma Workshop Consensus Panel 1. (Blood, 2011: 117; 4691-4695)

IMWG uniform response criteria by response subcategory for multiple myeloma

Response subcategory	Response criteria ^a	
sCR	CR as defined below plus	
	Normal FLC ratio (0.26-1.65) and	
	 Absence of clonal cells in bone marrow^b by immunohistochemistry 	
	or immunophenotyping ^c	
CR	 Negative IFE of serum and urine and 	
	 Disappearance of any soft tissue plasmacytomas and 	
	< 5% plasma cells in bone marrow ^b	
	 In patients in whom the only measurable disease is by sFLC levels, 	
	CR is defined as a normal FLC ratio (0.26-1.65) in addition to the CR	
	criteria listed above	
VGPR	 Serum and urine M-protein detectable by IFE but not on 	
	electrophoresis or	
	 90% or greater reduction in serum M-protein plus urine M-protein 	
	level < 100 mg per 24 h	
	 In patients in whom the only measurable disease is by sFLC levels, 	
	VGPR is defined as a >90% decrease in the difference between	
	involved and uninvolved sFLC levels	
PR	≥ 50% reduction of serum M-protein and reduction in 24-h urinary	
	M-protein by ≥ 90% or to < 200 mg per 24 h	
	 In patients in whom the only measurable disease is by sFLC levels, 	
	PR is defined as a ≥ 50% decrease in the difference between	
	involved and uninvolved sFLC levels	
	 If serum and urine M-protein are unmeasurable, and sFLCs are also 	
	unmeasurable, ≥ 50% reduction in bone marrow plasma cells is	
	required in place of M-protein, provided baseline percentage was ≥ 30%	
	 In addition to the above listed criteria, if present at baseline, a ≥ 50% 	
	reduction in the size of soft tissue plasmacytomas is also required	
SD ^d	Not meeting criteria for CR, VGPR, PR or progressive disease	

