Abbreviations: CR, complete response; FLC, free light chain; IFE, Immunofixation Electrophoresis; PR, partial response; SD, stable disease; sCR, stringent complete response; VGPR, very good partial response.

NOTE: Once (s)CR is established, response remains (s)CR until relapse is documented.

^a All response categories require two consecutive assessments made at anytime before the institution of any new therapy; all categories also require no known evidence of progressive or new bone lesions if radiographic studies were performed.

^b Confirmation with repeat bone marrow examination not needed.

^c Presence/absence of clonal cells is based upon the κ/λ ratio. An abnormal k/l ratio by immunohistochemistry and/or immunofluorescence requires a minimum of 100 plasma cells for analysis. An abnormal ratio reflecting presence of an abnormal clone is κ/λ of > 4:1 or < 1:2.

^d not recommended for use as an indicator of response; stability of disease is best described by providing the time to progression estimates

RELAPSE CRITERIA

Relapse subcategory	Relapse criteria	
Progressive disease ^a	Progressive Disease: requires one or more of the following:	
To be used for calculation of time to progression and progression-free survival end points for all patients including those in CR (includes primary progressive disease and disease progression on or off therapy)	 Increase of ≥ 25% from lowest response value in serum M-component (the absolute increase must be ≥ 0.5 g/dl)^b and/or Increase of ≥ 25% from lowest response value in urine M-component (the absolute increase must be ≥ 200 mg/24 h) and/or In patients in whom the only measurable disease is by sFLC levels, increase of ≥ 25% from lowest response value in the difference between involved and uninvolved sFLC levels (absolute increase must be >100 mg/L) If serum and urine M-protein are unmeasurable, and sFLCs are also unmeasurable, increase of ≥ 25% from lowest response value in bone marrow plasma cell percentage (absolute % must be ≥ 10%) Definite development of new bone lesions or soft tissue plasmacytomas or definite increase in the size of existing bone lesions or soft tissue plasmacytomas Development of hypercalcaemia (corrected serum calcium > 11.5 mg/dl or 2.65 mmol/l) that can be attributed solely to the plasma cell proliferative disorder 	
Clinical relapse ^a	Clinical relapse requires one or more of:	

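### For patients measurable only by serum free light chains (FLC), the Section 10.2 schedule omits the serial FLC values that Appendix C needs to score PR, VGPR and biochemical progression

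*Protocol*

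**What the plan says.** **Eligibility.** Section 8.1.1 requires "Measurable disease according to the IMWG criteria (see appendix A"). Appendix A lists several alternatives for measurable disease, any one of which suffices. One is "Abnormal FLC ratio with involved free light chain (FLC) > 100 mg/L". Only patients whose sole measurable parameter is a plasmacytoma are barred, and the stated reason is that their response is hard to evaluate.

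**Scoring.** For patients measurable only by serum FLC, Appendix C works with the gap between involved and uninvolved levels:
- PR: "PR is defined as a ≥ 50% decrease in the difference between" the two levels.
- VGPR: "VGPR is defined as a >90% decrease in the difference between" the two levels.
- Biochemical progression: "In patients in whom the only measurable disease is by sFLC levels, increase of ≥ 25% from lowest response value" in that difference, with an absolute rise above 100 mg/L.
- CR: a normal FLC ratio in addition to the other CR criteria.

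**Schedule.** Under Immunochemistry, Section 10.2 asks at entry for serum and urine M-protein "including immunofixation and FLC ratio". At evaluation it asks for serum and urine M-protein, immunofixation to confirm CR, and "FLC ratio only to confirm (s)CR".

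**Link between the two.** Section 10.3 says response is assessed by Appendix C after induction cycles 1, 3, 5, 7 and 9, through maintenance, at the end of protocol treatment and in follow-up.

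**The concern.** The schedule and the response criteria do not fit together for one eligible group. The word limiting FLC to (s)CR confirmation excludes serial testing. A ratio also gives the quotient of the two light chains, whereas Appendix C needs their difference.

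Three things depend on the missing values:
- **The induction primary endpoint** (Section 13.1) counts sCR, CR, VGPR and PR. An FLC-only patient in PR or VGPR could not be counted.
- **Entry to randomisation** (Section 8.2.1) needs at least a PR. Response is also a stratification factor (Section 15.2.2) and a covariate in the primary Cox model (Section 14.2.1).
- **PFS from randomisation** needs the date of progression. A biochemical relapse would not be seen when it happens.

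A statistical analysis plan cannot repair this, because it cannot recover assays that were never done.

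**Working it through.** **1. Is the gap closed elsewhere in the protocol?**
- Appendix C, in its practical details, requires testing at each evaluation for disease restricted to SPEP and for disease restricted to UPEP. It has no such line for FLC-restricted disease.
- The footnote there on light-chain escape is a good-practice remark that accepts either UPEP or FLC. It sets no schedule.
- Section 10.3 points to Appendix C but adds no test to Section 10.2.

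**2. What can still be scored for an FLC-only patient?**

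| Outcome | Input needed | Scheduled in 10.2? |
|---|---|---|
| sCR, CR | normal FLC ratio plus other criteria | yes, at confirmation |
| VGPR, PR | percentage fall in FLC difference | no |
| Biochemical progression | rise in FLC difference from lowest value | no |
| Progression by hypercalcaemia | calcium | yes, in blood chemistry |
| Progression by bone lesion or plasmacytoma | imaging | after induction, mainly on clinical indication or to confirm (s)CR; known plasmacytomas yearly |
| Death | survival status | yes |

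The loss is therefore confined to PR, VGPR and the biochemical route to progression.

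**3. The plan's own figures (Section 14.1).** Inputs: HR 0.39, two-sided alpha 0.05, power 0.90, 66% randomised, 80% response.
- Events by Freedman: (1.960 + 1.282)² × (1.39/0.61)² = 54.6, rounded up to 55. This agrees.
- Registered: 94/0.66 = 142.4, stated as 142. This agrees.
- Standard error of the response rate: √(0.80 × 0.20/142) = 3.4 points, stated as about 3.

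The point changes none of these figures.

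**4. Patients affected.** The documents give no FLC-only share, so 5-15% is an assumption: 142 × 0.05 = 7.1 and 142 × 0.15 = 21.3, or 7 to 21 registered patients.

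**5. Bias in the response rate.** Assume 80% true response in the FLC-only group, of which 25 percentage points are CR (also an assumption). PR and VGPR then make up 80 − 25 = 55 points, all unscored. Bias = share × 0.55:
- 5% share: 2.75 points
- 10% share: 5.5 points
- 15% share: 8.25 points

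At 10% the bias is 5.5/3.4 = 1.6 standard errors. It is systematic, so enrolling more patients would not reduce it.

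**6. Randomisation.** On the same assumptions, the unscored responders number 7.1 × 0.55 = 3.9 to 21.3 × 0.55 = 11.7, or about 4 to 12 patients who could be refused randomisation for want of a documented PR. Some would not have been randomised anyway, for other reasons.

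**7. PFS power, upper bound.** Suppose no PFS event at all is captured in the FLC-only group, the group makes up the same share of randomised patients, and follow-up is not extended. Power = Φ(√d × 0.61/1.39 − 1.960):
- 5% share: d = 52.25, power 0.89
- 10% share: d = 49.5, power 0.87
- 15% share: d = 46.75, power 0.85

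The true loss would be smaller, because non-FLC progression and death are still recorded and fewer such patients would reach randomisation.

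**The case against.** The strongest reply is that a site reading the whole protocol would measure FLC anyway. Section 10.3 binds it to Appendix C at each evaluation, and Section 16.1 says the CRF collects the parameters needed for response evaluation. On that view this is a drafting conflict rather than a design that leaves patients unassessable. That description is fair, but it does not remove the problem. Section 10.2 is explicit and restrictive, so practice could differ between centres, and Section 10.3 exposes the contradiction without resolving it.

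The second reply concerns the randomised comparison. Both arms share one schedule under double blinding, so the gap is not arm-specific by design. The final analysis waits for 55 events, and Section 14.1 allows registrations to be recalculated if too few patients are randomised. This stands: missed biochemical progression would mainly delay or misdate events in a small subset.

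A reader might infer more than the text supports:
- *That neither primary endpoint can be scored in these patients.* This does not follow. (S)CR rests on the FLC ratio, which is scheduled, and PFS events can still come from non-FLC progression or death.
- *That their progression is defined solely by FLC.* Appendix C asks for any one of several criteria. New or growing bone lesions, plasmacytomas and hypercalcaemia apply to them too.
- *That all of them fail the randomisation criterion.* Those in (s)CR pass. Nor can the full 5-15% share be applied to the 94 randomised if most of the group is not documented as responding. With only CRs captured at 25%, 7-21 registered patients give at most about 2-5 eligible on response.

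**Conclusion.** The conflict between Section 10.2 on one side and Section 10.3 with Appendix C on the other is real and should be corrected. For FLC-only patients, PR and VGPR cannot be scored from the scheduled tests, and biochemical progression would be missed or dated late. The main exposure is a downward bias in the induction response rate and wrongful exclusion of PR and VGPR patients from randomisation. The effect on PFS power is modest even at its upper bound.

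The existence of the conflict rests on the text alone. Its size rests on assumptions that the documents do not supply: the FLC-only share (5-15%), the CR rate in that group (25%), and sites following Section 10.2 literally. If sites measure FLC serially despite the schedule, the bias shrinks accordingly.

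**What to change.** Reconcile Section 10.2 with Section 10.3 and Appendix C:
- In Section 10.2 (Immunochemistry and the table footnotes), require quantitative involved and uninvolved serum FLC at entry and at every response evaluation in induction, maintenance and follow-up, for patients whose only measurable disease is by serum FLC. Keep the present restriction to (s)CR confirmation for everyone else.
- In Appendix C, beside the rule for SPEP- and UPEP-restricted disease, add the matching line for FLC-restricted disease.

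The cost is one sentence in each place and a small number of extra serum assays on blood already drawn at these visits.
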